A total of 150 subjects will be randomly assigned to 1 week of double-blind treatment with mifepristone 600 mg/d ($n=50$), 1200 mg/d ($n=50$) or placebo ($n=50$); all subjects will receive 8 weeks of counseling, 4 scheduled phone calls and a Week 12 follow up visit. Subjects will be medically healthy male or female volunteers, 18-65 years of age. Subjects must meet DSM-V criteria for current alcohol use disorder of moderate or greater severity, defined in DSM-V as ≥ 4 symptoms, because this is the level of severity likely to merit pharmacotherapy and to involve neuroadaptations in the stress systems that mifepristone is hypothesized to treat. Subjects must be abstinent ≥ 3 days (but ≤ 30 days) prior to randomization, as verified by the TLFB and BAC and have a CIWA ≤ 9 , to eliminate acute alcohol or withdrawal effects on study measures. Abstinence at randomization will be verified retrospectively by ethyl glucuronide/ethyl sulfate (EtG/Ets) testing, which can reliably detect alcohol metabolites in the urine 80 hours after alcohol consumption. EtG/Ets testing showed only 1 of 50 participants in our mifepristone lab study violated the 3-day abstinence requirement at baseline. Additionally, breathalyzer and Timeline Followback data are collected at every study visit; GGT data are collected monthly.

Inclusion Criteria:

- *Male or female volunteers, 18-65 years of age*
- *Meets DSM-V criteria for current alcohol use disorder of moderate or greater severity, defined by DSM-V as ≥ 4 symptoms*
- *In the month prior to screening, reports drinking > 21 standard drinks per week if male, > 14 if female, with at least one heavy drinking day (males: ≥ 5 drinks, females: ≥ 4 drinks) per week*
- *Seeking research-based outpatient treatment for AUD and willing to comply with the protocol, take daily oral medication for 1-week and complete 11 study visits*
- *Abstinent a minimum of 3 days (but not more than 30 days) prior to randomization*
- *Negative BAC and a CIWA score of ≤ 9 at randomization*
- *In acceptable health in the judgment of the study physician, on the basis of interview, medical history, physical exam, ECG, urine test and lab tests*
- *Females with childbearing potential must have a negative serum pregnancy test on the screening visit and a negative urine pregnancy test at randomization and agree to use non-hormonal effective birth control for the study duration and one month thereafter*

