- *Current use of drugs that are CYP3A substrates and inhibitors (such as calcium channel blockers, azole antifungals, macrolide antibiotics, erythromycin, protease inhibitors) due to risk of interactions with mifepristone; CYP3A inducers (such as rifampin, rifabutin, rifapentine, phenobarbital, phenytoin, carbamazepine, and St. John's wort), which may decrease mifepristone exposure and possibly compromise efficacy or consuming grapefruit juice or chronic use of drugs that are CYP2C8/2C9 substrates (such as NSAIDs, warfarin, and repaglinide), or as determined by the Study Physician*
- *No fixed domicile and/or no availability by home or mobile telephone*
- *Treatment mandated by a legal authority*

Subject Recruitment and Retention

This is the first test of the clinical efficacy of mifepristone for AUD, and as such, requires recruiting individuals with AUD who are both treatment-seekers and free from clinically significant medical and psychiatric disorders or use of concomitant medications that could influence study outcomes. Our experience conducting two N=150, 12-week clinical trials in AUD

with similar admission criteria at Scripps reliably shows we must recruit about 5 subjects for each subject who is successfully randomized, resulting in a rate of randomization of approximately 33 subjects per year. This rate of randomization is consistent with the average rate of 30-36 subjects randomized annually by single sites in recent AUD trials with similarly restrictive admission criteria.

Per procedures established by NIAAA's Clinical Investigations Group,⁴ progressive incentive payments will be provided for attendance and completion of study assessments to enhance compliance with study procedures and retention. Subjects will earn a base rate starting at \$25 that will increase by \$5 for each subsequent consecutive visit. The 4 weekly phone calls will be compensated at a flat rate of \$10 each. Perfect attendance and participation in 4 phone calls will result in a subject earning \$590 over the 12 weeks of study and follow up.

PROCEDURES

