Timeline Followback Interview (TLFB)¹² provides quantity and frequency estimates of alcohol consumption for the 90-day period prior to and throughout study. A standard drink is defined as 14g of absolute ethanol content which is equivalent to 12 oz beer, 1.5 oz hard liquor or 5 oz wine.¹⁰ A heavy drinking day is defined as ≥ 4 drinks per day for women and ≥ 5 for men.¹⁰ TLFB drinking data will be supported with weekly drinking diaries as a memory guide, and validated by weekly breathalyzer determination, and monthly GGT values. If unresolved inconsistencies between sources occur, then the most negative outcome will be assumed accurate. (Assessment Coordinator, 10 minutes at Week -1, 5 minutes thereafter).

Secondary Outcome Measures:

Alcohol Craving Questionnaire-Short Form (ACQ-SF)¹³ provides an assessment of current drinking urges, difficulty resisting urge and anticipation of positive outcome or relief from negative affective state by drinking (every study visit, 2 minutes). Neurocognitive Functioning The California Verbal Learning Test-II (CVLT-II)¹⁴ and the Verbal Fluency, Trail Making, Color-Word Interference, Design Fluency and Towers tests from the Delis-Kaplan Executive Function System (D-KEFS)¹⁵ and Letter Number Sequences from the Wechsler Adult Intelligence Scale-IV (WAIS-IV)¹⁶ will be used to measure aspects of executive functioning, learning and memory, which are thought to be impacted by the hypothalamic-pituitary-adrenal (HPA) axis and alcohol use and to expand on the mifepristone POC study findings (Weeks 0 and 8, Neuropsychologist, 45 minutes).

Exploratory Measures:

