Genetic Indicators of Mifepristone Effects Saliva samples will be collected using Oragene DNA (OG-500) 2 ml saliva kits (DNA Genotek, Inc) and genotyped on the Illumina Human Omni Express Exome beadchip, with analysis limited to selected candidate genes. Differences in response to mifepristone may also be reflected in cellular differences in response to the drug and to cortisol. To study this, blood samples will be collected and sent by same day transport to [name] Biochemical Genetics Laboratory at UCSD, which is located less than 1 mile from our lab and where peripheral white blood cells (PWBC's) will be extracted and cryopreserved. PWBCs will be isolated by density centrifugation through Nycoprep from whole blood (2 x 8ml) stabilized with acid citrate dextrose and stored at -140°C in tissue culture medium supplemented with 10% DMSO to maintain viability. [name] lab at NIAAA will generate lymphoblastoid cell lines and iPSC lines from cryopreserved PWBCs. Cell lines established from high and low responders to mifepristone will be analyzed for gene expression and methylation differences by RNA-seq and whole genome methylation analysis (Week 0, samples collected by Medical Technician). Cortisol and ACTH Blood is collected, spun, prepared, frozen and stored in [name] lab for periodic batch analysis in the [name]' lab using Enzyme Linked ImmunoSorbent Assay (ELISA) kits to provide quantitative determination of ACTH and cortisol in plasma (Weeks 0, 1, 2, 4, 8 and 12).

Safety Measures:

Breath Alcohol Concentrations (BAC) Subjects are informed prior to the screening visit that if they present with positive BAC's, they will not be paid and will be rescheduled, and have to wait until BAC is normal or will be accompanied home by a friend or taxi driver (beginning of every study visit, Research Nurse, 2 minutes). Adverse Event- Case Report form records each adverse event and onset, duration, severity, relation to study medication and clinical action (every study visit, Research Nurse, 5 minutes). Urine screen for illicit drug use (Weeks -1, 1, 4, 8 and 12).

PHARMACOTHERAPY CONDITIONS AND MEDICATIONS DISPENSED

Pharmacotherapy Conditions

Simple randomization procedures will be followed to randomly assign subjects to double-blind treatment with 600 mg/d or 1200 mg/d mifepristone or matched placebo in a 1:1:1 ratio, using a computer-generated randomization code provided by our laboratory biostatistician. Dose titration is not indicated.

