Rationale for Dose Selected

The daily doses selected (600 and 1200 mg) are consistent with those used in a recent large scale (N=433) efficacy and safety study of mifepristone for the treatment of psychotic depression¹⁷ which found no significant differences between mifepristone 600mg, 1200 mg and placebo for the percentages of patients with ≥ 1 adverse event or with serious adverse events. The most commonly reported side effects were: headache, dizziness and dyspepsia for mifepristone, and nausea and somnolence for placebo.

Rational for Study Duration

Dosing duration (1-week) provides a duration of drug exposure that is compatible with optimal drug effects for resetting the HPA axis and for maintaining subject safety.

Medication Supply

Mifepristone 300 mg tablets and matched placebo tablets will be provided by Corcept Therapeutics.

Medication Compliance

Subjects will receive a 1-week supply of double-blind study medication in a blister card package. Blistercards are consecutively numbered for each participant and prepared according to the randomization code. Neither subject nor study personnel involved in subject care or assessment will know the identity of the randomly assigned study drug. Medication will be identical in appearance and all subjects will be given the same number of double-dummy tablets to preserve the blind. Subjects will be instructed to take the study drug each morning, preferably with food, and to return the blistercard and any unused drug at the next visit (Week 1). A brief scripted phone call will be scheduled on Day 3 of medication to assess medication compliance, any AE's and subject concerns that could prompt study discontinuation. Compliance will be verified with returned medication package and pill count. Mifepristone plasma determinations will be obtained at Week 1 and will be analyzed retrospectively to verify correct medication assignment per the randomization code and ingestion of active medication and will be examined for an association with outcome.

Drug Accountability

All study medication is kept in a locked metal cabinet in the medication preparation room. The research technician labels and prepares the blinded medication in blistercards which are

identified by randomization code, and keeps a record of all medication dispensed and returned throughout the study.

Concomitant Pharmacological Treatments

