- Subjects will be provided with their Study Clinician's business card and a copy of the informed consent that includes 24/7 phone numbers for study physicians.
- Participants will be asked about adverse events and concomitant medications at the scheduled phone call on Day 3 of medication and at each study visit.
- Participants will be instructed about signs and symptoms of adrenal insufficiency and how to contact the study physician in case they occur. The following language will be used in the informed consent:

Tell your doctor right away if you have any of these symptoms:

- * Unusual tiredness or weakness
- * Nausea and/or vomiting
- * Dizziness when standing
- * Aches and pains
- * Loss of appetite
- * Being depressed

- Female participants will be instructed to report unexplained vaginal bleeding.
- Participants reporting symptoms of adrenal insufficiency or unexplained vaginal bleeding during the 1-week of study medication will be discontinued from study drug and seen promptly for medical evaluation.
- Laboratory evaluations and electrocardiogram will be repeated at the conclusion of medication to identify any abnormalities potentially related to drug exposure. Any clinically significant abnormalities persisting at the end of medication will be followed by the investigator until resolution or until a clinically stable endpoint is reached.
- Participants will be evaluated at the end of study medication for:
 - Evidence of QT prolongation (ECG) and if present will be monitored until resolution
 - Signs and symptoms of adrenal insufficiency. If adrenal insufficiency is suspected, it will be followed-up closely. *We note that no case of adrenal insufficiency or QT prolongation has been reported in studies of similar duration and dosing (also see Darpo et al., 2013).*

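### The no-pay, reschedule rule for a positive breath test continues after randomization, so payment and the timing of the Week 1 drug-level sample depend on drinking

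*Combined protocol and SAP*

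**What the plan says.** The rule is in the protocol under Outcome Measures and Assessments, Safety Measures. Subjects who present with a positive BAC are told that "they will not be paid and will be rescheduled, and have to wait until BAC is normal" or that they will be escorted home. The test is timed at the "beginning of every study visit, Research Nurse, 2 minutes". No distinction is made between visits before and after randomization.

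Four other places bear on it:

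- **Payment.** Subject Recruitment and Retention says that "progressive incentive payments will be provided for attendance and completion of study assessments to enhance compliance with study procedures and retention". The base is $25, rising by $5 "for each subsequent consecutive visit", and subjects must "complete 11 study visits".
- **Drug level.** Medication Compliance says that "Mifepristone plasma determinations will be obtained at Week 1 and will be analyzed retrospectively". One stated use is to look for an association with outcome. The SAP (second paragraph) lists plasma concentration as a predictor of response.
- **Safety checks.** The Data and Safety Monitoring Plan says that "Laboratory evaluations and electrocardiogram will be repeated at the conclusion of medication to identify any abnormalities potentially related to drug exposure".
- **Primary outcome.** The Timeline Followback (TLFB) is retrospective, covers the whole study, is supported by diaries and is "validated by weekly breathalyzer determination".

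The documents give no window for a rescheduled visit and do not say whether it is paid or keeps the step-up. They do not say that time since last dose is recorded with the drug level.

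**The concern.** Before randomization, turning away a subject with a positive breath test is an eligibility check. From Week 1 on, the same act makes payment and assessment timing a function of the outcome.

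This matters most for the concentration analysis. The one-week supply is taken each morning and the blister card is returned at Week 1, so dosing has ended or is ending when the sample is due. A later visit means a longer gap and a lower level. If the gap is longer because the subject had been drinking, the plan will see low level and heavy drinking together even when concentration has no effect. That is the direction the investigators expect: the Introductory Statement cites a concentration-drinking association in the proof-of-concept study as the reason for ranging doses. Neither retrospective drinking recall nor intention-to-treat analysis repairs it.

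Two lesser matters follow. Withholding pay from a subject who did attend works against the retention purpose of the payments, in a trial that already expects about 40% early termination. The end-of-medication ECG and laboratory tests would also move for these subjects.

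**Working it through.** **1. Payment ladder.** Eleven visits at $25, $30, ..., $75 sum to 11 × (25 + 75)/2 = $550. Four calls at $10 add $40. The total is $590, which matches the protocol. Week 1 is the third visit, worth 25 + 2 × 5 = $35. One positive test there costs:

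- $0 if the rescheduled visit is paid in full and the ladder is kept;
- $35 if only that payment is lost;
- $75 if it is unpaid and the ladder resumes at the missed step (the top step is never reached);
- $155 if it is unpaid and the ladder restarts at $25: 590 − (25 + 30 + 340 + 40), where 340 is eight visits at $25 to $60.

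The protocol does not say which applies.

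**2. Drug level after a delay.** Fraction remaining = 2^(−delay/half-life). The documents give no half-life, so 12 to 96 h is assumed.

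- One-day delay: 2^(−24/12) = 25% to 2^(−24/96) = 84%.
- Three-day delay: 2^(−72/12) = 2% to 2^(−72/96) = 60%.

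**3. False association.** Simulated: 50 subjects on drug with no true concentration effect. Drinks per week follow a gamma distribution with mean 8 and SD 12 (the high-dose mean and common SD under Sample Size). Log concentration has SD 0.4 (assumed). The chance of a positive Week 1 test is proportional to drinks per week, with the average set at the rate shown. In positive subjects, log concentration falls by ln 2 × delay/half-life. The correlation is tested two-sided at 0.05, so 5% is the correct rate.

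| Delay | BAC-positive | Half-life | False positives |
|---|---|---|---|
| Same day, 0–6 h | 5–20% | 24–72 h | 4–7% |
| One day | 2–5% | 48 h | 6–8% |
| 1–4 days, Week 1 and outcome drinking correlated 0.5 | 5–20% | 24–72 h | 8–37% |

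The first two rows use one drinking value both to trigger the positive test and as the outcome, which favours a false link. If the 1–4 day row did the same, it would run from 12% to 94%.

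**4. Primary comparison, if weeks were truly lost.** The plan's 91% power reproduces. The high-dose versus placebo difference is 16 − 8 = 8, with standard error 12 × √(2/50) = 2.4, and 8/2.4 − 1.96 = 1.37 gives 91.5%. Suppose 5% of placebo weeks and 2.5% of high-dose weeks were lost, each at 35 drinks (all assumed). The means become (16 − 1.75)/0.95 = 15.0 and (8 − 0.875)/0.975 = 7.3. The difference is 7.7 and power is 89.3%. This applies only if TLFB does not recover those weeks.

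**The case against.** The rule can be read more mildly. Subjects are told of it before screening, so it may have been written with screening in mind. Waiting until the BAC is normal can mean a same-day wait, which leaves the drug level almost untouched. Deferring assessment of an intoxicated subject is a reasonable safety step, and payment is for attendance and completed assessments, so withholding it when assessments are not done is no outright contradiction. These points limit the size, but the rule is timed at every visit and says without limit that the subject is rescheduled.

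A reader might infer more than the documents support:

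- **That primary-outcome data are lost.** The visit is postponed, not cancelled. TLFB can recover the missed days, and Weeks 9 to 11 are collected by phone without a breath test. Data are lost only if the subject does not return and is not reached.
- **That everyone who drank is affected.** Visits are typically at midday, and the test finds only alcohol present then.
- **That breath-test validation of TLFB is defeated.** The reading precedes any rescheduling, nothing says a positive is discarded, and unresolved conflicts go to the worse outcome.
- **That the later removal of the 600 mg arm rests on this analysis.** The amendment cites psychotic-depression literature.
- **That the extreme false-positive rates or a restarted payment ladder measure the problem.** Both rest on assumptions the documents do not supply.

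**Conclusion.** The point stands as a cheap improvement, not as a demonstrated bias in the treatment comparison. After randomization, the rule ties payment and visit timing to current drinking. For the concentration analysis, it makes the sampling time depend on the outcome, with no stated adjustment.

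The direction is clear: a spurious link between low level and more drinking. The size is not, because half-life, BAC-positive rate and delay are all assumed. It ranges from negligible with a same-day wait, through about 6% to 8% false positives for a one-day delay with 2% to 5% positive and a 48 h half-life, to clearly more with multi-day delays.

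The primary comparison between arms does not depend on the concentration analysis. For that comparison the remaining risk is non-return, which an unpaid visit may encourage but which the documents do not show.

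**What to change.** - Limit the no-pay and reschedule consequence to Week -1 and Week 0. Leave the wait-or-escort safety step unchanged.
- From Week 1 on, pay for attendance whatever the BAC result, and keep the consecutive-visit step-up.
- Draw the Week 1 plasma sample on the scheduled day where possible. Record the times of last dose and of sampling, and adjust concentration for time since last dose in the association analysis.
- When an interview is postponed, have TLFB cover every day back to the last interview.
- Reconcile the Safety Measures rule with the Data and Safety Monitoring Plan on the timing of the end-of-medication ECG and laboratory tests.

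The cost is a short change to the protocol and consent wording, two case report form fields, and a few payments for visits at which only part of the assessments is done.

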Statistical Plan

Glucocorticoid Antagonist Treatment of Alcohol Use Disorder

From NIH Grant Application #AA023152

P.I. [name].

Submitted 2/7/2014

All analyses will be conducted in the intention-to-treat sample with $p<0.05$ for two-tailed tests of significance. Demographics and baseline measures will be examined for differences between treatment groups and tested individually for correlation with each outcome. Any baseline variable significantly associated with outcome or differing between treatment groups will be included in subsequent analyses as a covariate. Trend dose effects will be determined using single or multi parameter tests of Mixed Effect Model (MEM) effects, as required. All MEMs are repeated measures centered on the relevant time period. Time, treatment, and time x treatment will be evaluated as fixed effects in each model.

Mifepristone plasma concentration and baseline drinking levels were significant predictors of response in our Proof of Concept (POC) study and will be evaluated as predictors in the proposed study. Sex, age, age of onset and family history of alcoholism will be examined as covariates of response because of a potential association with cortisol in the case of the latter 3 variables and to assess differential treatment response for males and females, given mifepristone's antiprogestrone effects, and the trend for females to have better drinking outcome in our POC study. Motivation, e.g., to have abstinence as a treatment goal, will be examined as a non-specific predictor of treatment outcome. Potential pharmacogenetic predictors of response will be evaluated on an exploratory basis.

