Furthermore, a collaboration with [name], Director, Neurogenetics Lab, NIAAA, will permit an exploratory evaluation of genetic predictors of response; the high affinity of mifepristone for the glucocorticoid receptor makes mifepristone a good candidate for pharmacogenetic analysis that may guide future studies and clinical applications.

GENERAL INVESTIGATIONAL PLAN

SUBJECTS

Sample Size

Power and sample size estimates are based on the change in the number of drinks per week found in our POC study that involved 1-week of mifepristone 600 mg/d vs placebo in 50 subjects with AUD and in our 12-week clinical trial of gabapentin 900mg, 1800mg and placebo in 150 subjects with AUD.² Repeated measures ANCOVA performed on the change in number of

drinks per week from baseline through Week 5 in the POC study found significant ($F=3.82$, $df=2$, $p=0.03$) slope effects between mifepristone (-9.19, SEM 7.5) and placebo (+3.62, SEM 7.5), yielding a Cohen's $d=0.485$ (medium effect size). Continuous outcomes will be assessed for trend dose effects. Based on estimates of change of 0, -2.2 and -6.7 (SE 1.6) drinks per week for placebo, 900mg and 1800mg, respectively, in our gabapentin study, the test for linear trend contrast resulted in highly significant ($p<0.001$) linear trends with post hoc power at least 99% at the target alpha. Power calculation of cumulative mean drinks per week vs. dose with a planned linear contrast indicates that with 50 subjects per arm (placebo, low dose, high dose), and means which decrease by at least 32% as dose increases, we achieve 91% power to detect a non-zero contrast of the means versus the alternative that contrast is zero using an F test. These calculations assume an alpha=0.05, a common SD \pm 12, and hypothesized means of approximately 16, 11 and 8 drinks per week based on the gabapentin data. Estimating early termination by approximately 40% subjects based on clinical trials of similar design,^{2,3} the same power analysis for a conservative total of 30 subjects per arm indicates 82% power to test the interactive term (week*treatment) at the alpha of 0.05.

Subject Characteristics

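### Simple randomisation does not reliably give the stated 50 per arm and leaves sex balance to chance; permuted blocks within sex would be a cheap, modest improvement

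*Combined protocol and SAP*

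**What the plan says.** The protocol's Pharmacotherapy Conditions section says "Simple randomization procedures will be followed to randomly assign subjects to double-blind treatment", to 600 mg/d, 1200 mg/d or "matched placebo in a 1:1:1 ratio, using a computer-generated randomization code provided by our laboratory biostatistician". Neither the protocol nor the SAP mentions blocking, stratification or minimisation.

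Subject Characteristics says "A total of 150 subjects will be randomly assigned to 1 week of double-blind treatment" and gives n=50 for each arm. The Sample Size section uses 50 per arm when it says "we achieve 91% power to detect a non-zero contrast of the means".

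The SAP lists sex among the covariates of response. Its reasons are to assess whether men and women respond differently and "the trend for females to have better drinking outcome in our POC study". It deals with imbalance only at analysis: a baseline variable becomes a covariate if it is significantly related to an outcome or differs between arms.

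Item 4.1 of the later modification request drops the 600 mg arm for the rest of the study. The documents give no new arm sizes or allocation method for that stage.

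**The concern.** The arm sizes in the sample-size argument are written as fixed, but under simple randomisation they are only expected values. The sex mix of the arms is also random, although the sponsor gives its own reasons for thinking that sex matters. Entry thresholds differ by sex as well (more than 21 drinks per week for men, more than 14 for women), so sex probably tracks baseline drinking, which the SAP reports as a significant predictor of response in the proof-of-concept study.

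At stake are some precision in the comparison of 1200 mg with placebo, the number of women per arm for the planned sex analysis, and whether sex enters the model by design or through a significance screen.

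**Working it through.** **Inputs from the documents.** N = 150, ratio 1:1:1, means 16, 11 and 8 drinks per week, SD 12, alpha 0.05 (Sample Size); two-tailed tests (SAP). The share of women is not given; 35-50% is assumed.

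**1. The plan's own figure.** For the linear contrast (-1, 0, 1) with 50 per arm:
- difference = 16 - 8 = 8
- SE = 12 × √(1/50 + 1/50) = 2.4
- noncentrality = 8 / 2.4 = 3.33, on 147 df
- power = 91.2%, so the stated 91% reproduces.

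**2. Arm sizes under simple randomisation.** These are multinomial (150; 1/3, 1/3, 1/3).
- SD of one arm's size = √(150 × 1/3 × 2/3) = 5.8; 95% range 39 to 61.
- P(exactly 50/50/50) = 150! / (50!³ × 3¹⁵⁰) = 0.55%.
- From 400,000 simulated allocations: the median gap between largest and smallest arm is 11; the gap is 10 or more in 61%; the smallest arm is 40 or fewer in 14%.

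**3. Effect on power.** Take placebo 40, 600 mg 60, 1200 mg 50. Then SE = 12 × √(1/40 + 1/50) = 2.55, noncentrality = 8 / 2.55 = 3.14, and power = 87.7%. Averaged over 5,000 simulated allocations, power is 90.8%, with a 5th percentile of about 88%. The mean loss is 91.2 - 90.8 = 0.4 points.

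**4. Sex balance (35-50% women assumed).** The share of women differs by 15 points or more between placebo and 1200 mg in 12-14% of trials, and between some pair of arms in 26-30%.

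**5. What a sex imbalance costs.**
- *Sex in the model.* The variance of the 1200 mg v placebo estimate rises from 1/n₁ + 1/n₂ to 1/n₁ + 1/n₂ + d²/S, where d is the difference in share of women and S = Σ n p(1 - p) over arms. With 50 per arm, shares of 0.325, 0.40 and 0.475, and so d = 0.15: S = 35.4, d²/S = 0.00064, against 1/50 + 1/50 = 0.04. The SE rises by about 0.8%. Over simulated allocations the rise averages 0.3%, with a 95th percentile of 1.3%.
- *Sex-by-treatment term.* Its SE rises by about 1.4-1.7% on average and 7-9% at the 95th percentile, including the effect of unequal arm sizes.
- *Sex not in the model.* With an assumed sex effect of 0.3 SD (3.6 drinks per week), a 15-point imbalance shifts the contrast by 0.15 × 3.6 = 0.54 drinks, against a difference of 8 and an SE of 2.4.

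**6. The alternative.** With permuted blocks of 6 within two sex strata (20,000 simulated trials for each assumed share of women), every arm has 48 to 52 subjects. The share of women differs by at most 4 points between arms. Exactly 50/50/50 occurs in about 39% of trials.

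**7. After the 600 mg arm closed.** The number randomised by then is not given. If it was 60 to 105 (assumed), placebo and 1200 mg already differed by 10 or more with probability 13-26%. For m further subjects allocated 1:1 by simple randomisation, the difference they add has SD √m. If the total stayed at 150, m is 45 to 90 and the SD is 6.7 to 9.5.

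**The case against.** The strongest reply is that little harm follows. Simple randomisation is unbiased, its variability is carried in the standard error, and n=50 can be read as a planning target. The large percentages in step 2 describe allocation; the power cost is 0.4 points on average. This stands, and it sets the size of the point. A reader might infer that the treatment comparison is biased or the trial underpowered by this choice; the documents and the figures above support neither.

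A second reply is that the SAP already provides for sex, since a covariate associated with outcome is admitted whether or not the arms differ. This stands in part. The admission depends on a significance test in the trial data, which is a weaker safeguard than pre-specification.

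A reader might also infer that stratifying by sex would stop chance imbalance from deciding the model. It would not: the SAP's rule screens all demographics and baseline measures, and stratification takes only sex out of the imbalance limb.

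On the choice of factor, the SAP reports baseline drinking as a significant predictor and sex only as a trend, so baseline drinking is a fair rival. Sex has the planned subgroup question in its favour and needs no cut-point.

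Finally, a fixed ratio, fixed n and a pre-generated code could describe a shuffled list with totals of 50. The word used points the other way. Such a list would give exact sizes only at full enrolment, would leave sex uncontrolled, and would not survive closure of an arm.

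**Conclusion.** The point holds as a modest improvement. The stated allocation method does not reliably produce the stated arm sizes, and it leaves to chance a factor that the SAP singles out. The allocation figures follow from N = 150 and 1:1:1 alone; the sex figures rest on the assumed 35-50% women, and the interim figures on an assumed 60 to 105 subjects at the change. The gain is in precision, balance and the planned sex analysis. It does not correct a bias, and the plan's 91% power is essentially intact. Blocking would bring the arms close to 50 without guaranteeing exactly 50, and after the 600 mg arm was removed no method gives 50/50/50 for the whole study.

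**What to change.** - In Pharmacotherapy Conditions, replace simple randomisation by computer-generated permuted blocks of concealed, randomly varying size, stratified by sex, and describe the expected arm sizes as approximately 50.
- For subjects randomised after the 600 mg arm was removed, use 1:1 blocks within sex, and state the new target sizes.
- In the SAP, make sex a fixed covariate in the primary model whatever the significance screen shows. The screen remains a separate problem for the other baseline variables and needs its own correction.
- If the code already in use is a fixed-total list, say so and correct the description.

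The cost is two sex-specific lists from the same biostatistician and two blistercard series in place of the single consecutive numbering described under Medication Compliance, with the right series chosen at dispensing. Allocation becomes slightly more predictable at a single site; the double-blind, double-dummy supply and varying block sizes limit that.
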